1. INTRODUCTION

1.1 Background and Rationale

Herpes simplex virus (HSV) infections are common and can cause significant morbidity both at the time of the original infection and when recurrences occur. There are two types of HSV – HSV-1 and HSV-2. HSV-1, the most common cause of oral “cold sores,” is transmitted mainly by oral-to-oral contact. Genital herpes is usually caused by HSV-2, although HSV-1 can also cause genital breakouts. Both HSV-1 and HSV-2 infections are lifelong, with the virus living in the ganglia of nerves that supply the area of the original infection and recurring sporadically in the same area of that nerve’s innervation. Most infections and recurrences are asymptomatic, but infectious viral shedding can occur. Patients who are not asymptomatic can develop prodromes of tingling, pain or paresthesia, and eventually blisters and ulcerations with pain. Healing generally occurs within 10 to 19 days after onset in primary infection or within 5 to 10 days in recurrent infection. Lesions usually heal completely, but recurrent lesions at the same site may cause atrophy and scarring.

According to WHO, in 2012 an estimated 3.7 billion people under age 50 (67%) had HSV-1 infection globally. Some patients have predictable outbreaks after exposure to noxious stimuli, such as sunlight fever, menstruation, or stress.

Researchers have found that calcium signaling is involved in the translocation of the virus from the ganglia to the eruption site. It has been found that an increase of calcium levels in the extracellular matrix will precipitate the calcium signaling events that are causal to the migration of the HSV virus from the proximal ganglia to the eruption site. (Hunsperger 2003, Cheshenko 2003) Further, Husperger found in her experiments (in vitro) that the chelation of calcium greatly reduced the reactivation of the HSV virus.

EDTA Eye Drops (EED), which consists of a calcium chelator and a permeation enhancer, could be one such intervention. Livionex has had some anecdotal evidence that this intervention could work at preventing an HSV eruption and post prodromal viral shedding.

IRB-approved clinical studies of HSV-1 have been performed in normal human volunteers with a history of HSV-1, who develop recurrences with prodromes after exposure to UV light. We will use this technique to induce recurrences in susceptible, HSV-1 infected individuals then treat with EED or Comparator 5 times daily.

Abreva® has been chosen as the Comparator product in this study because it is approved by the FDA for treatment of HSV-related cold sores. Dosing 5 times/day has been selected as the dosing regimen because that is the dosing regimen approved for Abreva by FDA. The manufacturers of Abreva recommend that subjects not be treated for greater than 10 days. A maximum of 7 days treatment with study product has been chosen for this study.

Thus, treatment in both groups of subjects, will be 5 times daily and will last until healing of the lesion, or up to 7 days following the onset of the prodrome.

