	
study medication and instructed how to apply it to the exposed area. When the patient first senses the start of developing a cold sore and applies study medication will be considered Day 1. Dosing of the study product will be done five times daily, beginning at the time that a subject first senses the start of the prodromal phase (Day 1). Subjects will be given a diary card to record their pain levels, progression of lesion development and any unusual symptoms (not normally seen with their outbreaks).
 
Patients will be called daily by the study team after their induction visit to determine the start of prodrome. If after 7 days, the patient does not develop any prodromal senses, the patient will be considered an induction failure.
 
When the patient first senses signs or symptoms of a cold sore, they will have the Day 1 visit conducted within 24 hours. Day 1 visit may be conducted in person or as a MyChart Virtual Visit. Their diary card will be reviewed and if they have experienced a prodrome and/or lesion since the induction visit, their compliance with dosing will be checked. If the subject has noted any unusual symptoms, these will be discussed with medical personnel to determine if the symptoms represent a treatment emergent AE. A photo will be taken of the irradiated area (as marked at the induction visit). The blinded assessor will assess the prodrome and/or lesion and take measurements.
 
On Days 3, 5, and 7, the subject will return to the clinic or follow up via virtual video call for assessment of the irradiated area. Study staff will review the subject diary to determine if the subject is correctly noting the lesion stage. Subjects will have a photo taken of the radiated area and asked to continue with dosing as instructed. Any diary card notation of unusual symptoms in subjects will be reviewed by study staff to determine if the symptoms represent a treatment emergent adverse event. The blinded assessor will assess the prodrome and/or lesion and take measurements. More study product may be dispensed as needed. Most subjects' lesions will have resolved by day 7, and they will end study treatment after 7 full days of treatment. If lesion has not resolved by day 7, the maximum number of days the patient may use study drug treatment is 10 days.
 
The EOS is the final study visit will take place on Day 10. A photo will be taken of the irradiated area, the diary card will be carefully reviewed and study product (including empty containers) will be collected. If subjects reach EOS without full resolution of their lesion(s), they will be given the option to begin taking a prn medication for the remainder of the outbreak. Measurements will be taken. If an adverse event has occurred but has not resolved by the EOS visit, the subject will be contacted once weekly and status noted until such time as the event has resolved. The blinded assessor will assess the prodrome and/or lesion.
 
A Safety follow-up phone call will occur 2 days after the EOS to determine if any new AEs have occurred.
 
Safety will also be evaluated by an independent physician throughout the study. The first independent safety evaluation will be done once 5 subjects

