--	--

[figure not shown]
	have reached EOS. Thereafter, the independent safety evaluation will occur as each subsequent group of 5 subjects reaches EOS and will include data on all subjects having reached EOS.
Enrollment Period	Subjects will be enrolled over a 2 year period.
Treatment Period	Subjects will be treated for up to 7 days from the time they first experience a prodrome and/or a lesion. If lesion has not resolved by day 7, the maximum number of days the patient may use study drug treatment is 10 days. If subjects reach EOS without full resolution of their lesion(s), they will be given the option to begin taking a prn standard of care medication for the remainder of the outbreak. Subjects that do not exhibit a prodrome within 7 days of the induction visit, will be considered induction failures and be discharged from the study. Total time of study participation for any given subject may range from 13 to 25 days.
Location	University of Utah MidValley Clinic, Department of Dermatology
Safety Assessments	Solicited AEs by review of diary cards and discussion with subjects
Efficacy Assessments	Primary: 
Number of subjects that experience prodrome (Stage 1) but do not progress to vesicles (Stage 3) by completion of treatment Secondary: 
Subject-assessed duration of painClinician-assessed duration of lesion appearance (Stage 3), as reported by subject, to complete healing (Stage 5)Measurement of cumulative lesion area (all eruptions if more than 1)Measurement of each lesion (if more than one) from eruption (Stage 3) through healing of hard crust (Stage 4) to identify the largest lesion

TABLE OF CONTENTS

PROTOCOL SYNOPSIS	ERROR! BOOKMARK NOT DEFINED.
1. INRODUCTION	1
1.1 Background and Rationale	1
2. OBJECTIVE	2
2.1 Efficacy Endpoints	2
2.1.1 Primary:	2
2.1.2 Secondary:	2
2.2 Safety Endpoint	2
3. STUDY DESIGN	2
4. STUDY TREATMENT	4
4.1 EDTA Eye Drops	Error! Bookmark not defined.
4.2 Comparator: Abreva®	4
4.3 Randomization Codes	4
5. SUBJECT POPULATION	4
5.1 Inclusion Criteria	4
5.2 Exclusion Criteria	5
6. STUDY PROCEDURES	6
6.1 Study Visits	6
6.1.1 Screening Visit (Days -14 to 0)	6
6.1.2 Study Day 1 Visit (Baseline)	Error! Bookmark not defined.
6.1.3 Study Days 3 and 5 Visits	8
6.1.4 Study Day 7 +/- 1 day Visit	8
6.2 Study Day 10 Visit	Error! Bookmark not defined.
6.2.1 End of Study (EOS) Visit	Error! Bookmark not defined.
6.3 Early Discontinuation Visit	9
7. EFFICACY EVALUATIONS	9

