Patients will be called daily by the study team after their induction visit to determine the start of prodrome. When the patient first senses the prodromal phase, they need to be seen within 24 hours for the Day 1 visit. Patients that do not have prodromal senses within 7 days of the induction will be considered induction failures. Induction failure patients will be asked to return their study drug to the study team.

On Days 1, 3, 5, and 7 the subject will follow up in person or via virtual MyChart visit with blinded assessor during which the subject's diary card will be reviewed and compliance with dosing checked. If the subject has noted any unusual symptoms, these will be discussed with medical personnel to determine if a treatment emergent adverse event has occurred or, if the subject has not started treatment, whether their medical history should be updated. If possible, the lesion will be measured. A photo will be taken of the irradiated area (as marked at the induction visit). More study drug may be dispensed as needed. Most subjects' lesions will have resolved by day 7, and they will end study treatment after 7 full days of

treatment. If lesion has not resolved by day 7, the maximum number of days the patient may use study drug treatment is 10 days. An end of study (EOS) visit will occur as soon as their lesion is healed or Day 10, whichever comes first.

The EOS visit (Day 10) is expected to be the final study visit. EOS will occur when a subject's lesion is fully healed or Day 10 (whichever comes first). A photo will be taken of the irradiated area, the diary card will be carefully reviewed and study product (including empty containers) will be collected. Subjects who developed a lesion that has not yet healed will be given the option to begin taking a prn medication that has been previously prescribed to treat an outbreak.

If an adverse event has occurred but has not resolved by the EOS visit, the subject will be contacted once weekly, and status of the AE noted until such time as the event has resolved.

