6.1.4 Study Days 3, 5, and 7 Visits

On Days 3, 5, and 7, the subject will present for a follow up appointment in clinic or via virtual video call consisting of:

- Review of the subject’s diary card to identify possible treatment emergent adverse events.
- Assessment of the subject’s pain on a visual analog scale.
- Measurement of the lesion will be taken (if lesion is present).
- Photographs of area exposed to UV radiation may be asked to be taken by subjects and uploaded into their MyChart account. If patients are present in clinic, photographs will be taken by study staff.
- If the subject has experienced a prodrome or lesion they should have started dosing. The study staff will review their dosing compliance and examine the study product tube/bottle. If the subject is not complying with the dosing regimen, the study staff will determine whether non-compliance is serious enough to warrant terminating the subject’s participation. Otherwise, minor non-compliance should be noted, and the subject should be retrained on how to dose themselves.

Once patients reach the Stage 2/3 lesion their lesion may be swabbed for viral culture (HSV PCR). If the patient reaches Stage 2/3 over the weekend, the lesion will not be swabbed. We will reserve this for the first five patients but may continue to do all patients to ensure lesion is in fact a cold sore and not a reaction to the UV radiation.

6.1.5 EOS – End of Study Visit (Day 10 – or after subject’s lesion has fully healed)

An EOS visit will occur after the subject’s lesion has fully healed or Day 10 (whichever comes first), the subject will present to the clinic for a follow up appointment in clinic or via virtual video call consisting of:

- Review of the subject’s diary card to identify possible treatment emergent adverse events. If the subject has an AE that has not resolved by this time, the site staff will explain to the subject that they will be called every week to check on the status of the AE, until it is resolved.
- Assessment of the subject’s pain on a visual analog scale.

- Photographs of area exposed to UV radiation may be asked to be taken by subjects and uploaded into their MyChart account. If patients are present in clinic, photographs will be taken by study staff.

The subject's diary card and all tubes//bottles of study product (empty, partially used or unused) will be collected and the subject will be released from the study.

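### Dosing is capped at 7 days in the rationale and schedule but extendable to 10 in the design, and the t-test on episode duration has no value for a subject unhealed at end of study

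*Combined protocol and SAP*

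**What the plan says.** **Length of dosing.** The synopsis rationale and section 1.1 both state: "A maximum of 7 days treatment with study product has been chosen for this study". The schedule in section 10 puts the end of dosing in its Day 7 column, and Day 10/EOS is a separate column. The synopsis (Design and Treatment Period rows) and section 3 give a different rule: "If lesion has not resolved by day 7, the maximum number of days the patient may use study drug treatment is 10 days".

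**Stopping at healing.** Section 1.1 says that treatment "will last until healing of the lesion, or up to 7 days following the onset of the prodrome". The synopsis Design row and section 3, speaking of subjects whose lesions have resolved by Day 7, say "they will end study treatment after 7 full days of treatment".

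**EOS timing.** The synopsis Design row says "The EOS is the final study visit will take place on Day 10". Section 3 says the "visit will occur as soon as their lesion is healed or Day 10, whichever comes first", and section 6.1.5 agrees: "lesion has fully healed or Day 10 (whichever comes first". Section 6.1.5 also has all study product collected at that visit.

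**Episode duration.** Section 7.1 has photographs from Day 1 through EOS reviewed against the diary's date of healing or seven full treatment days. It then defines outbreak duration as running from prodrome to healing. Section 9.2 compares episode duration between arms by a two-sample t-test and plans Kaplan-Meier methods for time to lesion healing. It gives no rule for a subject unhealed at EOS.

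**The concern.** For two ordinary kinds of subject, no single course of action satisfies every section. One is unhealed at Day 7: must dosing stop, or may it continue to Day 10? The other heals before Day 7: does dosing stop then, or run to seven full days? The amount of product used would depend on which section the site happened to read.

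The analysis problem is separate. A t-test needs one number per subject. The protocol itself provides for lesions still open at EOS, and for those subjects the time from prodrome to healing has not been observed. Without a stated rule, such subjects must be either dropped, which removes the longest episodes, or given their EOS time, which understates the episode. Either handling pulls an arm's mean down by an amount that depends on how many of its subjects are unhealed.

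**Working it through.** The plan has no figure of its own on this point to reproduce.

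**Inputs**
- Applications per day: 5 (synopsis; sections 1.1 and 3).
- Dosing caps: 7 days (section 1.1; section 10) and 10 days (synopsis; section 3).
- Day 1 is the first day of dosing (synopsis Design row; section 3).
- Usual healing time of a recurrence: 5 to 10 days (section 1.1).
- Assumption: all five applications are made on every treated day, with Day 1 counted in full.

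**1. Subject unhealed at Day 7.** Applications = 5 × days treated.
- 7-day cap: 5 × 7 = 35.
- 10-day cap: 5 × 10 = 50 at most.
- Difference: 50 − 35 = 15 at most.

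**2. Subject healed at Day 5** (the low end of the section 1.1 range).
- Dosing stops at healing: 5 × 5 = 25.
- Seven full days: 5 × 7 = 35.
- Difference: 35 − 25 = 10.

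The seven-day course cannot be completed if EOS follows section 3 or 6.1.5, because the product is then collected at healing. It can be completed only if EOS waits until Day 10, as in the synopsis Design row.

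**3. The rules side by side**

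| Place | Cap if unhealed at Day 7 | If healed early | EOS |
|---|---|---|---|
| Synopsis rationale; section 1.1 | 7 days | stop at healing | not stated |
| Synopsis Design row | 10 days | 7 full days | Day 10 |
| Synopsis Treatment Period row | 10 days | not stated | not stated |
| Section 3 | 10 days | 7 full days | healing or Day 10 |
| Section 6.1.5 | not stated | product collected at EOS | healing or Day 10 |
| Section 10 | Day 7 | not stated | Day 10/EOS column |

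**4. How many subjects.** The documents do not say. The 5-to-10-day range makes healing on either side of Day 7 ordinary, but the protocol expects most lesions to have resolved by Day 7. A uniform spread over 5 to 10 days would put (10 − 7)/(10 − 5) = 60% after Day 7, which contradicts that expectation, so it is not used as an estimate.

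**5. Episode duration.** For a subject unhealed at EOS (Day 10), duration is known only to exceed the time from prodrome to EOS. Nothing in the section 9.1 populations removes such a subject. Kaplan-Meier can use this partial information, and section 9.2 already plans it for time to healing. The t-test cannot.

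**6. Primary outcome.** The synopsis and section 7.1 tie non-progression to the end of treatment, which may be Day 7 or Day 10. The choice matters only for a subject below Stage 3 at Day 7 who first shows vesicles on Days 8 to 10; 0 or 1 such subject is assumed.

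**The case against.** The strongest reply is that the intended cap is easy to infer. The synopsis Design row, the synopsis Treatment Period row and section 3 all give 7 days with extension to 10, and the Treatment Period row puts both figures together. Section 1.1 is rationale, and the schedule is a summary grid that also omits Day 3. The extension also stays within the 10-day limit that section 1.1 attributes to the comparator's manufacturers. This stands as evidence of intent and lowers the weight of the point. It does not reconcile a stated maximum of 7 days with "the maximum number of days the patient may use study drug treatment is 10 days", and it does not settle what early healers do.

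A reader might infer that section 7.1 closes the episode at Day 7 for anyone still unhealed, so that up to 10 − 7 = 3 days are lost per subject and a difference between arms shrinks. The text does not support this. Section 7.1 defines duration as running to healing and has photographs reviewed through EOS. The seven-day phrase is best read as a stray anchor left from the 7-day cap.

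A reader might also add that the investigator, who is unblinded, or a designee judges the duration. That is true under any wording of the end date, and the change proposed here does not cure it, so it carries no weight in this point.

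Two further cautions stand. Episode duration is named only in section 9.2, and equating it with the outbreak duration of section 7.1 is an inference. The listed secondary endpoint, lesion duration, already runs to healing and is not in question.

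**Conclusion.** The dosing and EOS rules conflict in current text. Per affected subject the gap is 35 against up to 50 applications if unhealed at Day 7, or 25 against 35 if healed at Day 5, assuming full compliance. No shift between arms is claimed, because the number of affected subjects is not given and the same rules apply to both arms.

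The t-test on episode duration is unsuitable for subjects unhealed at EOS, whom the protocol expressly expects. How far this matters depends on how many there are, and the documents do not say. The effect on the primary outcome is a minor matter of definition. Overall severity is minor to moderate.

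**What to change.** Make one protocol amendment.

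- **Dosing:** adopt the rule in the synopsis Design and Treatment Period rows and section 3 (7 days, extendable to Day 10 if unresolved), and state that dosing stops at healing. Align the synopsis rationale, section 1.1 and section 10, and qualify the seven-full-days wording in the synopsis Design row and section 3.
- **EOS:** change the synopsis Design row to healing or Day 10, whichever is earlier.
- **Episode duration:** remove the seven-day phrase from section 7.1. Run duration from prodrome to healing, and censor unhealed subjects at the last lesion assessment (EOS, at most Day 10). Say what counts as healing for a subject who never reaches Stage 3.
- **Analysis:** in section 9.2, replace the t-test for episode duration with Kaplan-Meier estimates and a log-rank test. The test must be named, because the section names none for its Kaplan-Meier analysis.
- **Schedule:** clear or explain the photograph and lesion-measurement marks under the phone call two days after EOS, so that the censoring time is unambiguous.
- **Primary outcome (minor):** define progression as Stage 3 at any time from Day 1 through EOS.

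Most of this is wording. No visit is added, since section 10 already schedules lesion measurement and blinded rating at Day 10/EOS. There are three costs: the sponsor must commit to a regimen for early healers, vesicles first seen on Days 8 to 10 count as progression, and episode duration is no longer reported as a simple difference in means.

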2. OBJECTIVE

To collect preliminary efficacy and safety data on the use of EED in subjects with a history of herpes labialis, following UV Radiation

2.1 Efficacy Endpoints

2.1.1 Primary:

- Proportion of subjects using EED v. those using the Comparator, who do not progress to Stage 3 (vesicle) of a herpes labialis outbreak following UV radiation exposure

2.1.2 Secondary:

- Pain in the lip and surrounding area
- Duration of lesion until healed (loss of hard crust)
- Cumulative lesion area (sum of all lesions)
- Maximum lesion size (size of the largest lesion)

2.2 Safety Endpoint

Adverse events

3. STUDY DESIGN

This will be a randomized, efficacy assessor-blinded, parallel group, pilot study of up to 20 subjects with documented UV induced herpes labialis. We will enroll until we have 20 subjects that have expressed a lesion from the induction and complete the treatment period of the study. With the possibility of screen failures and induction failures, we may consent up to 35 patients maximum.

Potential subjects will be assessed during a screening visit that must take place no greater than 2 weeks prior to the Induction visit. During the screening period, subjects that meet all other entry criteria will undergo UV susceptibility testing to determine their individual MED (minimal erythema dose). UV susceptibility testing takes place over two days with exposure to UV light on specified regions on the subject's back followed by an assessment of the exposed areas 24 hours later to identify the MED.

Subjects who have a measurable MED will be allowed to enroll in the study. Each subject will be randomly assigned in a 1:1 ratio to receive either EED or Comparator.

Subjects that do not have a measurable MED will be considered screen failures or may have repeat MED testing with new values.

At the Induction Visit, subjects will undergo UV radiation at a level 3 times their MED. The exposed area of the lip will be marked with indelible ink and a baseline photograph may be taken.

Each subject will then be randomly assigned in a 1:1 ratio to receive either EED or Comparator. Subjects will be dispensed study medication and instructed how to apply it to the exposed area. Dosing of the study product will be done 5 times daily, beginning at the time that a subject first senses the start of the prodromal phase (Day 1). The EED is a clear viscous eye drop, and the Comparator is a white cream substance. Therefore, the subject and principal investigator will be unblinded, and only efficacy assessments will be done by a qualified trained blinded assessor.

Subjects will be given a diary card to record their pain levels (starting at Day 1), progression of lesion development and any unusual symptoms (not normally seen with their outbreaks).

Patients will be called daily by the study team after their induction visit to determine the start of prodrome. When the patient first senses the prodromal phase, they need to be seen within 24 hours for the Day 1 visit. Patients that do not have prodromal senses within 7 days of the induction will be considered induction failures. Induction failure patients will be asked to return their study drug to the study team.

On Days 1, 3, 5, and 7 the subject will follow up in person or via virtual MyChart visit with blinded assessor during which the subject's diary card will be reviewed and compliance with dosing checked. If the subject has noted any unusual symptoms, these will be discussed with medical personnel to determine if a treatment emergent adverse event has occurred or, if the subject has not started treatment, whether their medical history should be updated. If possible, the lesion will be measured. A photo will be taken of the irradiated area (as marked at the induction visit). More study drug may be dispensed as needed. Most subjects' lesions will have resolved by day 7, and they will end study treatment after 7 full days of

treatment. If lesion has not resolved by day 7, the maximum number of days the patient may use study drug treatment is 10 days. An end of study (EOS) visit will occur as soon as their lesion is healed or Day 10, whichever comes first.

The EOS visit (Day 10) is expected to be the final study visit. EOS will occur when a subject's lesion is fully healed or Day 10 (whichever comes first). A photo will be taken of the irradiated area, the diary card will be carefully reviewed and study product (including empty containers) will be collected. Subjects who developed a lesion that has not yet healed will be given the option to begin taking a prn medication that has been previously prescribed to treat an outbreak.

If an adverse event has occurred but has not resolved by the EOS visit, the subject will be contacted once weekly, and status of the AE noted until such time as the event has resolved.

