6.1.2 Induction Visit

Upon reporting to the clinic for their induction visit, the subject will be randomized to receive either EED or Abreva. The following assessments will then be performed to establish baseline values prior to dosing:

- Review of Medical History and Concomitant Medications for any changes between Screening and Day 1 (Treatment emergent AEs are collected in this study beginning with first instance of dosing. Any unusual symptoms prior to the start of dosing will be recorded, if appropriate, as an update to the subject's medical history).

- Limited Physical Exam to check for any changes between Screening and Day 1(changes in PE after start of dosing will be assessed as possible treatment emergent AEs)

If the subject remains qualified for the study:

- They will be dispensed study product (EED or Abreva) and instructed to use it 5 times daily beginning when they first sense a prodrome or see a lesion (they will be asked to note the day and time of their first dose on their diary card).
- They will be given a diary card and instructed how to complete it. A practice diary completion may be done to ensure that subjects know how to complete the diary.

Subjects will then be discharged from the clinic with an appointment to return on Day 3 via virtual video call. They will be instructed to bring their Diary Card and the tube/bottle of study product that they have received.

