9. STATISTICAL METHODS

9.1 Analysis Populations

Analysis populations are defined as follows:

- The Safety population will include all subjects who use EED or Abreva for at least one day.
- The Per Protocol population will include all subjects (that were not induction failures) who complete the study, defined as attending all study visits.

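### Subjects know their arm before they give the self-report that decides whether they are analysed, and the timing of randomisation is stated inconsistently

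*Combined protocol and SAP*

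**What the plan says.** **Knowledge of the arm.** Product is dispensed at the Induction Visit. Section 3 explains that one product is a clear viscous drop and the other a white cream, and concludes: "Therefore, the subject and principal investigator will be unblinded, and only efficacy assessments will be done by a qualified trained blinded assessor".

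**Entry to the analysis.** Dosing starts when the subject first senses a prodrome; Section 6.1.2 adds seeing a lesion. The study team learns of it by daily telephone call. Section 3 then states: "Patients that do not have prodromal senses within 7 days of the induction will be considered induction failures". Section 9.1 defines two sets. Per Protocol will "include all subjects (that were not induction failures) who complete the study", which it defines as attending every visit. Safety requires at least one day of product use. Section 9.2 does not say which set the primary comparison uses, and no all-randomised set is defined.

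**Primary measure.** Section 7.1 counts subjects who have a prodrome (Stage 1) and do not reach vesicles (Stage 3) by the end of treatment.

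**Timing of randomisation.** In the Synopsis and Section 3, after the UV exposure has been described: "Each subject will then be randomly assigned in a 1:1 ratio to receive either EED or Comparator". In Section 6.1.2: "Upon reporting to the clinic for their induction visit, the subject will be randomized to receive either EED or Abreva". That sentence is followed by "The following assessments will then be performed to establish baseline values prior to dosing", meaning the review of history and medications and the limited examination. Product is dispensed under the condition "If the subject remains qualified for the study". Section 4.3 has the Investigator generate a simple randomisation code and describes no concealment step.

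**The concern.** Blinding the assessor protects the staging of lesions. It does not protect the step before that, which is deciding who is in the denominator. That step rests on a subjective sensation reported by someone who already knows which product they hold.

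The primary measure makes this step matter. A faint tingle that comes to nothing is scored as a success if the subject reports it and doses. If the subject lets it pass, the same tingle becomes an induction failure and leaves the analysis. A small difference between arms in the threshold for reporting therefore goes straight into the primary proportion. With roughly ten subjects per arm, one or two such reports are visible in the result.

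The conflicting randomisation timings raise a smaller, separate issue. Under Section 6.1.2 the allocation exists before continued eligibility is confirmed, and the Investigator holds the code. The arm could then be known to staff while they decide whether a subject stays in.

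**Working it through.** **1. Does every analysis set depend on the self-report?**
- Per Protocol excludes induction failures, and induction failure is defined by no reported prodrome within 7 days.
- Safety requires product use, which begins only when the subject senses a prodrome or sees a lesion.
- No other set is defined.

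So the answer is yes, whichever set Section 9.2 intends. Product is not applied before the first sign, so the true occurrence of prodrome should not differ by arm. The bias can come only through knowledge of the arm.

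**2. Size of the effect (illustration).** The plan gives no event rate, alpha or sidedness, so there is no plan figure to reproduce. The assumptions are:
- 10 genuine prodromes per arm (half of the target of 20; simple randomisation does not guarantee an even split);
- the same true non-progression rate p in both arms, varied from 20% to 50%;
- k extra reports in one arm that never reach Stage 3;
- a chi-square test at two-sided 0.05.

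The apparent rate in the affected arm is (10p + k)/(10 + k), so the shift is k(1 − p)/(10 + k). For k = 2 this is (1 − p)/6. At p = 40% the apparent rate is (4 + 2)/12 = 50%, a shift of 10 points.

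For the error rates, let a and b be the genuine non-progressors in the two arms, each binomial(10, p). The probabilities of all pairs (a, b) are summed where the test on a + k of 10 + k against b of 10 exceeds 3.84 and favours the affected arm.

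| True rate | Apparent rate, k = 2 | Shift (points) | Uncorrected, k = 0 → k = 2 | Continuity-corrected, k = 0 → k = 2 |
|---|---|---|---|---|
| 20% | 33.3% | 13.3 | 1.5% → 10.2% | 0.4% → 1.5% |
| 30% | 41.7% | 11.7 | 1.9% → 8.1% | 0.6% → 1.9% |
| 40% | 50.0% | 10.0 | 2.0% → 6.6% | 0.6% → 2.0% |
| 50% | 58.3% | 8.3 | 2.1% → 6.0% | 0.6% → 2.1% |

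At p = 40%, one, two and three extra reports give apparent rates of 45%, 50% and 54%. The uncorrected error rates are 4.6%, 6.6% and 9.0%.

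**3. What an all-randomised analysis would do.** In one arm let n be randomised, g have a genuine prodrome, s of those not progress, and k be doubtful reports that do not progress.
- As planned: (s + k)/(g + k). Numerator and denominator both move with k.
- Rule A, induction failures counted as not achieving the outcome: (s + k)/n. The denominator is fixed and a progressor is never a success, but the numerator still moves by k/n.
- Rule B, induction failures counted as not progressing to Stage 3: (n − (g − s))/n. There is no k in it, so reporting or not reporting a doubtful prodrome changes nothing.

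Rule A guards against subjects dropping out of the denominator. Rule B guards against arm-dependent reporting. Both are needed.

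**4. The timings.** Section 6.1.2 places randomisation on arrival and the recheck after it. The Synopsis and Section 3 place randomisation after UV exposure. Both cannot be followed. Both precede the prodrome, so reconciling them does not by itself cure the main problem.

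**The case against.** The best defence has four parts.
- The product must be in the subject's hands before the prodrome, because dosing starts at the first sign.
- There are partial safeguards. Inclusion criterion 8 requires subjects who usually have prodromes; the team calls daily; the Day 1 visit follows within 24 hours; and the Synopsis and Schedule of Assessments have the blinded assessor rate at Day 1 (Section 7.1 says from Day 3).
- A subject who goes on to a lesion starts dosing anyway, so the exposure is mainly to prodromes that come to nothing.
- This is a pilot with no stated alpha, so error rates matter less than the estimate.

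Much of this stands. The problem is confined largely to doubtful, non-progressing prodromes, and the shift in the estimate is the more relevant figure. But such prodromes are exactly what the primary measure counts as successes. The assessor is given no say in who counts as having had one. And product in hand need not be product identified.

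A reader might also infer more than the documents support:
- *That the subject learns the arm before eligibility is rechecked.* Section 6.1.2 dispenses only after the recheck. At that point only staff knowledge is possible, and the documents do not say who does the recheck.
- *That staff who know the arm deliver the UV exposure.* No passage says who delivers it, and its level is tied to the subject's own MED.
- *That there are three conflicting randomisation timings.* The first allocation sentence in Section 3 carries no time word and can be read as a general statement. Two timings clearly conflict.
- *That the bias favours EED.* The comparator is an approved cold-sore product, so expectation could run either way.

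**Conclusion.** The concern holds. As written, the plan lets a report made with knowledge of the arm decide who contributes to the primary proportion, and neither defined population avoids this. The direction is not fixed by the documents.

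The size is illustrative. Two extra reports in one arm would move its rate by 8 to 13 points. They would raise false significant results favouring that arm from about 2% to 6-10% without continuity correction, and only to about 2% with it. These figures rest on the assumed 10 per arm, rates of 20% to 50%, number of extra reports and two-sided 0.05. The weakness in the design does not rest on them.

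That Per Protocol is the efficacy set is an inference, since Section 9.2 names none; the conclusion is the same for Safety. The conflict in randomisation timing is real but secondary. The change should be made before enrolment continues.

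**What to change.** 1. State one randomisation point: the last step of the Induction Visit, after the eligibility recheck and UV exposure. Align Sections 3 and 6.1.2 to it.
2. Dispense in sealed, opaque, numbered kits with instructions inside, opened only once the first sign has been recorded with date and time. When dosing starts is left unchanged. This protects the call-based ascertainment only if whoever makes the calls does not hold the code.
3. Report induction failures by arm, and name the primary efficacy population in Section 9.2.
4. Add an all-randomised sensitivity analysis under both scoring rules, applied identically in each arm: induction failures counted as not achieving the primary outcome, and induction failures counted as not progressing to Stage 3.

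Cost: opaque packaging, reworded visit text and two extra tabulations. Application training must cover both products or move into the kit. The all-randomised analyses dilute any true effect, so they serve as a check and do not replace the main comparison.
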